## 2.3 Hypothesis

The purpose of this study is to explore the effects of ANB020 300 mg/100mL IV administration compared to placebo on eosinophilia, FEV1, and FeNO in adult patients with severe eosinophilic asthma.

## 2.4 Risk-Benefit Assessment

A patient with eosinophilic asthma may or may not benefit from participating in this study. However, based upon the inhibition of IL-33 by the investigational product (IP) and pre-clinical study results, patients with eosinophilic asthma may benefit. Participation in this study may help to develop important scientific knowledge that could contribute to the development of a new medication and better comprehensive treatment of patients who suffer from asthma, atopic dermatitis, or food allergies.

ANB020 has been extensively tested in animals, and was found to be safe and well tolerated in a Phase I SAD study (ANB020-001) conducted in healthy subjects. In animal studies, there were no ANB020 related adverse events (AEs) or abnormal ECG findings and the administration of ANB020 had no effect on hematology, coagulation, clinical chemistry, or urinalysis test results. In the Phase I study (ANB020-001), 64 healthy subjects were enrolled and dosed in the SAD part. The doses implemented in the SAD study were 10, 40, 100, and 300 mg SC and 40, 100, 300, and 750 mg IV. No significant changes in the vital signs (BP, HR, or body temperature), physical examinations, or ECGs were noted. The most commonly reported TEAEs were upper respiratory tract infection (50% versus 48% in placebo and ANB020 group, respectively) and headache (31% versus 27% in placebo and ANB020 group, respectively). A total of 44% subjects in the placebo as well as ANB020 group had study drug related TEAEs. One SAE of decreased neutrophils was reported in the ANB020 750 mg dose group which resolved without sequelae prior to study completion. This event was also considered a serious unexpected adverse reaction and was deemed possibly related to the study treatment. No other observations of decreased neutrophils lower than  $1.5 \times 10^9/L$  were observed. One subject in the ANB020 40 mg dose group, had an increased troponin level which returned to normal prior to study completion. No other significant changes in the laboratory test results were noted.

Although nothing in the testing of ANB020 to date indicates that an allergic reaction is likely; a reaction to any drug is possible. Some symptoms of allergic reactions are rash, wheezing or difficulty breathing, dizziness or fainting (also a possible outcome of a drop in BP), swelling around the mouth, throat or eyes, a fast pulse, or sweating.

As ANB020 is a mAb, based on clinical studies with other mAbs, study participants may experience symptoms of an apparent allergic reaction to the drug, also known as ‘cytokine release syndrome’. The symptoms of this vary dramatically but can include:

- Mild to moderate fever, chills, headache, nausea, and vomiting.
- Moderate to severe symptoms such as edema, hypotension, and pulmonary infiltrates (e.g. blood and mucus in the lung).

## **3.0 STUDY OBJECTIVES**

### **3.1 Primary Objectives**

The primary objectives of the study are as follows:

- To measure the reduction of eosinophils (blood eosinophil count) from Baseline (Day 1 pre-dose) to Day 22 in adult severe eosinophilic asthma patients administered with ANB020.
- To assess the safety and tolerability of a single, IV dose of ANB020 compared to placebo in adult patients with severe eosinophilic asthma.

### **3.2 Secondary Objectives**

The secondary objectives of the study are as follows:

- To measure the reduction of eosinophils (blood eosinophil count) from Baseline (Day 1 pre-dose) to the End of Study (EOS) visit (Day 127) in adult severe eosinophilic asthma patients administered with ANB020.
- To assess the change from Baseline in the clinic FEV1 from Baseline (Day 1 pre-dose) to the EOS visit (Day 127).
- To assess the change from Baseline in FeNO in the breath from Baseline (Day 1 pre-dose) to the EOS visit (Day 127).
- To assess the PD activity of ANB020 on ex vivo induced IFN- $\gamma$  levels.
- To test for any immunogenicity to ANB020.
- To describe the limited PK of ANB020 following a single, IV dose in adult patients with severe eosinophilic asthma.

### **3.3 Exploratory Objectives**

The exploratory objectives of the study are as follows:

- To assess the effect of ANB020 on circulating serum cytokines.
- To assess the activity of ANB020 after a single, IV dose on clinical scores such as the Asthma Control Questionnaire (ACQ), Patient Global Impression of Change (PGIC), and the Clinical Global Impression of Change (CGIC).

- To assess the effect of ANB020 on the asthma symptoms, change in standard of care (SOC) treatment, and rescue medication (short-acting beta-agonists [SABA]) usage.
- To assess the effect of ANB020 on IgE levels.

## 4.0 INVESTIGATIONAL PLAN

### 4.1 Summary of Study Design

This is a Phase IIa, double-blind, placebo-controlled, proof of concept study designed to assess the effects of a single 300 mg/100 mL IV dose of ANB020 compared to placebo in adult patients with severe eosinophilic asthma. This study will also assess the safety and tolerability of ANB020 in adult patients with severe eosinophilic asthma.

A written informed consent will be obtained from each patient prior to completing any study procedures. At the Screening visit (7-14 days before Day 1) inclusion and exclusion criteria will be assessed. Medical history, ongoing medications, as well as vital signs will be recorded. Various other study assessments including a physical examination, FeNO measurement, spirometry to determine FEV1, and laboratory tests will be performed (See Table 4.1 for study procedures and time points).

On Day 1, patients will present to the study center, and the inclusion and exclusion criteria will be verified. Eligible patients will be randomized to receive one IV dose of either ANB020 (300 mg/100 mL) or placebo (0.9% sodium chloride [100 mL]) in a 1:1 ratio. Specific study assessments (See Section 6.0) and safety laboratory tests (See Table 4.1) will be performed. Blood samples to determine eosinophil count (See Table 4.1), ex vivo induced IFN- $\gamma$  levels, anti-drug antibodies (ADA), serum cytokines, and serial samples for PK analysis will be collected at specified time points (See Section 18.0). Patients will remain in the study center for approximately 6 to 8 hours to complete the study assessments. Patients with any ongoing AEs or SAEs at the time of scheduled discharge from the study center should remain at the study center until the Investigator has determined that these events have been resolved or deemed as not clinically significant.

After completing the Day 1 assessments, all patients will be followed up period for 18 weeks. During the follow-up period, patients will return to the study center for study assessments on Day 2, 8, 22, 36, 64, 85, and 106 and will be contacted via telephone by study staff on Day 50 and 57 (See Table 4.1 for study procedures and time points). The EOS visit will be on Day 127 (Week 18) at the study center (See Table 4.1).

[figure not shown]
All patients will undergo FeNO and FEV1 tests at each study center visit. An ACQ (See Section 13.0) will be completed by all patients at each study center visit except (Day 2) and the patient diary must be completed on a daily and weekly basis. The Investigator will rate the patient's response using the CGIC scale and the patients will be asked to rate the degree of change in the overall asthma status using the PGIC scale (part of the diary card [See Section 6.0

for description and Table 4.1 for instructions]). The PGIC and CGIC scales are presented in Section 14.0 and Section 15.0, respectively. During the follow-up period, other assessments including vital signs, safety laboratory testing, eosinophil count, PK, and biomarker analysis will be performed at specified time points (Table 4.1).

The study design is presented in Figure 4.1 and the Schedule of Events is presented in Table 4.1.

**Figure 4.1 Schematic of Study Design for Protocol ANB020-004**

Abbreviations: PK = pharmacokinetics; n = sample size

**Table 4.1 Schedule of Events**

Assessment Days	Screening 7-14 days prior to Day1	Day 1	Day 2	Week 1 Day 8	Week 3 Day 22	Week 5 Day 36 (+/-2 days)	Week 7 Day 50 (Phone) (+/-2 days)	Week 8 Day 57 (Phone) (+/-2 days)	Week 9 Day 64 (+/-2 days)	Week 12 Day 85 (+/-2 days)	Week 15 Day 106 (+/-2 days)	Week 18 EOS Day 127/ET g (+/-2 days)
General Assessments												
Informed Consent	X i	X a										
Medical History/Demographics	X											
Inclusion/Exclusion Criteria	X	X e										
Clinical Observations												
Exhaled change in nitric oxide (FeNO)	X	X e	X	X	X	X			X	X	X	X
FEV 1 (Spirometry) j	X	X e	X	X	X	X			X	X	X	X
Patient and study staff completed: Asthma Control Questionnaire j	X	X e		X	X	X			X	X	X	X
Patient Diary k	X	X	X	X	X	X	X	X	X	X	X	X
Investigator's assessment (CGIC) j			X	X	X	X			X	X	X	X
Safety Assessments												
Physical Examination	X											X
Safety Laboratory b	X	X e	X	X	X	X			X	X	X	X
Hematology Panel for Eosinophils c	X	X e	X	X	X	X			X	X	X	X
Vital Signs	X	X	X	X	X	X			X	X	X	X
Urinalysis	X								X	X	X	X
Serum Pregnancy Test (WOCBP Only) b	X		X	X	X	X			X	X	X	X
Urine Pregnancy Test (WOCBP Only)		X e										
FSH d	X											
12-Lead ECG	X											X
Concomitant Medications	X	X	X	X	X	X	X	X	X	X	X	X
Adverse Events h	X	X	X	X	X	X	X	X	X	X	X	X
Virology, TB screening, and Drugs of abuse screen	X b											
Samples for ADA f		X e		X		X				X	X	X

Assessment Days	Screening 7-14 days prior to Day1	Day 1	Day 2	Week 1 Day 8	Week 3 Day 22	Week 5 Day 36 (+/-2 days)	Week 7 Day 50 (Phone) (+/-2 days)	Week 8 Day 57 (Phone) (+/-2 days)	Week 9 Day 64 (+/-2 days)	Week 12 Day 85 (+/-2 days)	Week 15 Day 106 (+/-2 days)	Week 18 EOS Day 127/ET g (+/-2 days)
PK/PD/Biomarker Assessments												
Samples for PK f		X	X	X	X	X			X			
Whole blood sampling for ex vivo induced IFN- $\gamma$ f		X e										X
Serum Sampling for Biomarkers Cytokines f (IL-33, IL-4, IL-5, IL-9, IL-13, sST2)		X e	X	X	X	X			X			X
IP administration												
Administration of ANB020 or Placebo		X										

Abbreviations: ADA = anti-drug antibody; CGIC = Clinical Global Impression of Change ECG = electrocardiogram; EOS = End of Study; ET = Early Termination; FeNO = fractional exhaled nitric oxide; FEV1 = forced expiratory volume in 1 second; FSH = follicle stimulating hormone; IL = interleukin; IFN- $\gamma$  = interferon-gamma; IP = investigational product; PD = pharmacodynamics; PK = pharmacokinetics; TB = tuberculosis; WOCBP = women of childbearing potential

- a Confirm informed consent and continued willingness to participate.
- b See Table 7.1 for safety laboratory details (Virology, QuantiFERON® TB Gold test, and drugs of abuse to be performed at screening only). Serum pregnancy for WOCBP will be performed at all study center visits except Day 1. On Day 1, urine pregnancy test will be performed prior to IP administration.
- c Sample for eosinophil count will be obtained as part of the standard hematology safety laboratory panel at each study center visit.
- d The FSH levels will be obtained only on postmenopausal patients defined as aged over 45 years with at least 1 year of amenorrhea. Blood samples to determine the FSH levels will be obtained only at screening.
- e Complete prior to IP administration on Day 1.
- f See Section 18.0 (Appendix VI) for PK, IFN- $\gamma$ , ADA, and biomarker cytokines collection time points. On Day 1, PK samples will be collected prior to IP administration as well as post-dose as specified in Section 18.0 [Appendix VI].
- g ET visit will include all procedures to be done at EOS visit as well as any procedures that should be done at the next regularly scheduled visit (Please collect sample for PK analysis if the ET visit occurs between Day 1 to Day 64). ET visit will be performed if the patient discontinues the study before EOS visit. If the patient completes all study visits and return to study center for EOS visit on Day 127, ET visit will not be applicable.
- h Patients with any ongoing AEs or SAEs at the time of scheduled discharge from the study center on Day 1 should remain at the study center until the Investigator has determined that these events have been resolved or deemed as not clinically significant.
- i ACQ and CGIC scales must be completed prior to blood draw/lab assessments and other procedures such as FeNO, FEV1 on each study center visit. On Day 1, the applicable scales and questionnaire must be completed prior to IP administration as well as prior to laboratory assessments and other study procedures.
- j Both pre- and post-bronchodilator spirometry (FEV1) should be performed at every clinic visit. Please refer to Section 6.1.2 for details.
- k Patient Global Impression of Change (PGIC) scale will be a part of the patient diary card and the scale should be completed after receiving IP (i.e. after Day 1). Additional instructions will be provided in the patient diary card.
- l Informed consent can occur prior to the -14 day Screening Visit. Note: consenting must occur prior to conducting any study procedures.

## 4.2 Discussion of Study Design

ANB020 is a first-in-class, anti-IL-33 therapeutic antibody developed by AnaptysBio, to treat Th2 cell driven inflammatory diseases with underlying IL-33 dysregulation. Preliminary evidence of this compound's significant PD activity in terms of cytokine modulation has been demonstrated in non-clinical and clinical studies, justifying its further development in patients with eosinophilic asthma.

Emergent data of the Phase I study (ANB020-001) in healthy subjects are the basis for the dose and IV route of administration of ANB020. The 300 mg IV dose was found to be safe and well tolerated in healthy subjects. In the SAD part of the study, 64 subjects were enrolled and dosed. The doses implemented in the SAD part were 10, 40, 100, and 300 mg SC and 40, 100, 300, and 750 mg IV. No significant changes in the vital signs (BP, HR, or body temperature), physical examinations, or ECGs were noted. The most commonly reported TEAEs were upper respiratory tract infection (50% versus 48% in placebo and ANB020 group, respectively) and headache (31% versus 27% in placebo and ANB020 group, respectively). A total of 44% subjects in the placebo as well as ANB020 group had study drug related TEAEs. One SAE of decreased neutrophils was reported in the ANB020 750 mg dose group which resolved without sequelae prior to study completion. No other observations of decreased neutrophils lower than  $1.5 \times 10^9/L$  were observed. One subject in the ANB020 40 mg dose group, had an increased troponin level which returned to normal prior to study completion. No other significant changes in the laboratory test results were noted.

The dose of ANB020 selected for this study 300 mg/100 mL (IV) has provided complete inhibition of IL-33 induced cytokine release (ex vivo) up to 84 days and has been administered safely in study ANB020-001.

Eosinophilic asthma is a Th2 associated atopic disease. Patients with eosinophilic asthma have been demonstrated to have improved FEV1 and reduced exacerbations when treated with anti-IL5 medications, which reduce eosinophil levels. Interleukin-33 is upstream of IL-5 in the Th2 cytokine cascade. Inhibition of IL-33, through the use of ANB020, would be expected to reduce IL-5, as well as other Th2 inflammatory mediators (such as IL-4 and IL-13 also successfully targeted in Th2 asthma), resulting in reduced asthma symptoms and eosinophil levels and improved lung function.

## 4.3 Selection of Study Population

Eligibility criteria for this study have been carefully considered to ensure the safety of the patients included in the study and that the results of the study can be used. It is imperative that patients fully meet all of the inclusion criteria and none of the exclusion criteria.

### 4.3.1 Inclusion Criteria

Patients will be enrolled in the study only if they meet all of the following criteria:

- Male and female patients aged  $\geq 18$  to  $\leq 65$  years and able to give informed consent.
- Patients with a confirmed clinical diagnosis of eosinophilic asthma with peripheral eosinophils count  $\geq 300$  cells/ $\mu\text{L}$  at screening.
- Twelve months history of diagnosis of eosinophilic asthma (with asthma exacerbation within the last 12 months [before screening] requiring rescue medication).
- Severe asthma diagnosed according to the Global Initiative for Asthma (GINA) 2016 requiring GINA treatment steps 3 to 5 (See Section 16.0).
- Pre-bronchodilator FEV1 of  $< 80\%$  at screening.
- Body mass index (BMI) of 18 to 38 kg/m^2 (inclusive) and total body weight  $> 50$  kg (110 lb.). BMI = weight (kg)/(height [m^2]).
- Women of childbearing potential (WOCBP) must have a negative serum pregnancy test at screening and a negative urine pregnancy test on Day 1 and be using highly effective methods of contraception (See Section 4.3.4) or be surgically sterile, or be postmenopausal throughout the study and for 18 weeks after the last dose of IP administration. Postmenopausal patients defined as (1) aged over 45 years with at least 1 year of amenorrhea and levels of follicle-stimulating hormone (FSH) over 20 IU/L at screening or (2) aged over 50 years with at least 1 year of amenorrhea.
- Male patients must be willing to use effective methods of contraception during the entire study period and for 18 weeks after the last dose of IP administration (See Section 4.3.4).
- Patient must be on high dose ICS plus LABA (See Section 5.8.2 for high dose guidelines). Systemic corticosteroids (intramuscular or oral) up to the equivalent of 15 mg/day prednisone will be allowed.
- Willing and able to comply with the study protocol requirements.
- Have the ability to read and understand the study procedures and can communicate meaningfully with the Investigator and staff.

### 4.3.2 Exclusion Criteria

Patients will not be enrolled in the study if they meet any of the exclusion criteria:

- Have concomitant medical condition(s) which may interfere with the Investigator's ability to evaluate the patient's response to the IP.
- Have experienced severe life-threatening anaphylactic reactions.
- Have received any IP within a period of 3 months or 5 half-lives of an IP (whichever is longer) before screening (this also includes investigational use of marketed products).
- Have received high dose systemic corticosteroids (equivalent to >15 mg/day prednisone), nonsteroidal, immunosuppressant, or immunomodulating treatments within 8 weeks before screening.
- Have received treatment with biologics such as mepolizumab or omalizumab within 3 months or 5 half-lives (whichever is longer) before screening.
- Abnormal ECG assessment at screening (any abnormality that the Investigator believes is not safe for study participation).
- Uncontrolled hypertension, or acute ischemic cardiovascular diseases.
- Have received antibiotic treatment within 4 weeks before screening.
- Have a history of hypersensitivity or allergic reactions to polysorbate 80, a component of the ANB020 formulation or the inactive ingredients (excipients).
- If female, is pregnant or lactating, or intend to become pregnant during the study period.
- History (or suspected history) of alcohol or substance abuse as defined by the Diagnostic and Statistical Manual of Mental Disorders (5th edition) Substance Use Disorders guidelines within 2 years before screening.
- Current smokers or former smokers with a smoking history of  $\geq 15$  pack years. If a patient has less than 15 pack years smoking history, he or she should have quit smoking at least 6 months before screening to enroll in the study.
- Positive blood screen for hepatitis C virus antibody, hepatitis B virus surface antigen, human immunodeficiency virus 1 and 2 antibodies, or *Mycobacterium tuberculosis* (TB). Patients with an indeterminate QuantiFERON® TB Gold result at screening will be allowed one retest; if not negative on retesting, the patient will be excluded.
- Any co-morbidity that the Investigator believes is a contraindication to study participation. This includes, but not limited to any respiratory (e.g. pulmonary fibrosis, eosinophilic granulomatosis with polyangiitis [EGPA], allergic bronchopulmonary aspergillosis [ABPA]), cardiovascular, gastrointestinal, hematological, neurological,

immunological, musculoskeletal, renal, infectious, neoplastic, or inflammatory condition that may place the safety of the subject at risk during the study, influence the results of the study or their interpretation, or prevent the patient from completing the entire duration of the study.

- Have any other physical, mental, or medical conditions which, in the opinion of the Investigator, make study participation inadvisable or could confound study assessments.
- Receipt of a live attenuated vaccine within 4 weeks before screening.
- Planned surgery during the study or 30 days before screening.
- History of malignancy within 5 years, except non-melanoma skin cancer which has been fully treated with no current active disease.

#### **4.3.3 Disease Diagnostic Criteria**

Adult patients (age  $\geq 18$  to  $\leq 65$  years) with a confirmed clinical diagnosis of eosinophilic asthma with a documented blood eosinophil count of  $\geq 300$  cells/ $\mu\text{L}$  despite receiving SOC treatment.

#### **4.3.4 Patient Restrictions**

The following restrictions may affect patient participation in this study:

- Availability to attend visits according to the protocol.
- Concomitant medication restrictions as described in Section 5.8.
- Restricted alcohol intake ( $< 28$  units per week).
- Strenuous exercise should be avoided up to 72 hours before the planned study visits.
- WOCBP must follow a consistent and correct use of highly effective methods of birth control during the study period and for 18 weeks after the last dose of IP administration.
- Male patients must be willing to use contraception throughout the study and for 18 weeks after the last dose of IP administration which includes a total of 5 half-lives of the IP (estimated to be approximately 70 days) plus an additional 50 days (which includes the duration of sperm turnover) post treatment completion. Additionally, female partners of male patients must also use highly effective methods of contraception if she is a WOCBP.

Patients must agree to the use of one method of highly effective contraception as listed below:

### **Highly Effective Methods of Contraception**

- Hormonal methods of contraception include oral contraceptive pills, vaginal ring, injectables, implants, and intrauterine systems (IUS) such as Mirena®.
- Non-hormonal intrauterine devices (IUDs)
- Bilateral tubal ligation
- Vasectomy

Acceptable alternate methods of highly effective contraception must be discussed with the Investigator to ensure highly effective methods of contraception are instituted prior to the patient receiving any dose of IP.

### **Less effective methods of contraception**

- Diaphragm
- Cervical cap
- Vaginal sponge
- Male condom\*
- Progestin only pills by male patient's WOCBP partner
- Female condom\*

\*A male and female condom must not be used together.

### **Patient Restrictions Prior to Lung Function Assessments**

- Patients should avoid engaging in strenuous exertion for at least 30 minutes prior to all lung function assessments.
- Patients should avoid eating a large meal for at least 2 hours prior to all lung function assessments.

#### **4.3.5 Patient Withdrawal**

All patients are free to withdraw from participation in the study at any time, for any reason, specified or unspecified, and without prejudice to further treatment. The inclusion and exclusion criteria are to be followed explicitly. If a patient who does not meet the enrollment criteria is inadvertently enrolled, that patient should be withdrawn from the study. AnaptysBio and IQVIA

must be contacted, and if the patient has received ANB020 or placebo, the patient must be followed up until EOS (Day 127) for any AEs and/or SAEs.

In addition, the patients will be withdrawn from the study under the following circumstances:

- Prior to IP administration, the Investigator decides that the patient should be withdrawn or is at risk. If this decision is made because of an AE or a clinically significant laboratory value, the IP should not be administered and appropriate measures are to be taken. AnaptysBio and/or IQVIA is to be notified immediately.
- The patient is unwilling to continue in the study.
- Lack of compliance with protocol.
- The Investigator or AnaptysBio, for any reason, stops the study.
- If a female patient becomes pregnant.
- New information suggests taking part in the study may not be in the participant's best interest.

Patients who discontinue the study early will have early termination (ET) procedures performed as shown in Table 4.1 (Schedule of Events).

Patients who are withdrawn from the study after Day 36 will not be replaced. All patients who discontinue the study prior to completing the Day 36 study assessments will be replaced. The study pharmacist should also be notified of any patient who has received IP and discontinues prior to Day 36.

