## **5.6 Selection and Timing of Dose for Each Patient**

Patients will receive a single dose of ANB020 or placebo administered under supervision at the study center. The infusion will be administered at the rate of 100 mL per hour via a Baxter infusion solutions set (FNC2110; prime volume 16 mL) or equivalent followed by a 16 mL IV saline flush, at the same infusion rate, to ensure that no residual drug remains in the infusion line. No in-line filter is to be used. Infusions will be administered over 1 hour. The ANB020 or placebo infusion may be slowed or interrupted for patients experiencing infusion-related AEs.

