## **5.8 Prior and Concomitant Treatments**

### **5.8.1 Excluded Medications**

The following medications will not be permitted during the study. Use of these excluded medications is a protocol deviation and should be recorded in the electronic case report form (eCRF).

- Treatment with systemic corticosteroids (intramuscular or oral) equivalent to >15 mg/day prednisone, nonsteroidal, immunosuppressant or immunomodulating drugs within 8 weeks before screening and throughout the study.
- Any antibiotic treatment within 4 weeks before screening.
- Use of biologics such as mepolizumab or omalizumab within 3 months or 5 half-lives (whichever is longer) before screening and throughout the study.
- Any live attenuated vaccine within 4 weeks of screening and for the duration of the study (Day 127).

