### 9.1 Determination of Sample Size

The number of patients to be enrolled is not based on statistical power considerations.

A total of approximately 24 patients will be randomized in a 1:1 ratio to receive ANB020 or placebo.

All patients who discontinue the study prior to completing the Day 36 study assessments will be replaced. Patients who are withdrawn from the study after Day 36 will not be replaced.

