APPENDIX 2. PROGRAMMING CONVENTIONS FOR OUTPUTS

IQVIA Output Conventions

Outputs will be presented according to the following Global Bios > Processes > GBIOS Processes -

Document: \\ieedc-vnasc01\biosdata\AnaptysBio\ANB020\CYA74392\Biostatistics\Documentation\SAP\Final\20181218 Version Number: 1.0 Author:

Version Date: 18Dec2018

Template No: CS_TP_BS016 Revision 4 Reference: CS_WI_BS005

Effective Date: 01Apr2016

29 June 2020 43

Implementation Guidelines and Templates > General Guidelines and Templates > Output Conventions

Dates & Times

Depending on data available, dates and times will take the form yyyy-mm-ddThh:mm:ss

Spelling Format

English UK

Presentation of Treatment Groups

For outputs, treatment groups will be represented as follows and in that order

Treatment Group	For Tables, Listings and Graphs	Treatment Number
ANB020	Dummy1	1
Placebo	Dummy2	2

Presentation of Visits

For outputs, visits will be represented as follows and in that order:

Long Name (default)	Short Name	Visit Number
Screening (Day 0)	Scr	1
Baseline (Day 1)	BL	2
Day 2	Day002	3
Day 8, week 1	Day008	4
Day 22, week 3	Day022	5
Day 36, week 5	Day036	6
Day 64, week 9	Day064	7
Day 85, week 12	Day085	8
Day 106, week 15	Day106	9
Day 127, week 18 (EOS/ET)	EOS	10

For outputs, visits for PK/PD will be represented as follows and in that order:

Document: \\ieedc-vnasc01\\biosdata\AnaptysBio\ANB020\CYA74392\Biostatistics\Documentation\SAP\Final\20181218

Author:

Version Number: 1.0 Version Date: 18Dec2018

Reference: CS_WI_BS005

Template No: CS_TP_BS016 Revision 4

Effective Date: 01Apr2016

CONFIDENTIAL

STATISTICAL ANALYSIS PLAN

AnaptysBio Inc PROTOCOL ANB020-004 Page 44 of 46

Visit	РК	Ex vivo induced INF-γ	ADA	Cytokines
Day 1	Pre-dose (-0.5 hours) 0.5 hours post SOI EOI EOI+3 hours EOI+6 hours	Pre-dose (-0.5 hours)	Pre-dose (-0.5 hours)	Pre-dose (-0.5 hours)
Day 2	24 hours post SOI	1		24 hours post SOI
Day 8, week 1	168 hours post SOI	168 hours post SOI	168 hours post SOI	168 hours post SOI
Day 22, week 3	504 hours post SOI	1	1	504 hours post SOI
Day 36, week 5	840 hours post SOI	840 hours post SOI	840 hours post SOI	840 hours post SOI
Day 64, week 9	1512 hours post SOI			1512 hours post SOI
Day 85, week 12		2016 hours post SOI	2016 hours post SOI	
Day 106, week	1	2520 hours post SOI	2520 hours post SOI	
Day 127, week 18 (EOS/ET)		3024 hours post SOI	3024 hours post SOI	3024 hours post SOI

Listings

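### Protocol 4.3.5 withdraws dosed patients found ineligible or non-compliant, which ends scheduled outcome measurement after one early termination visit although a single-dose study has no treatment left to stop

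*Protocol*

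**What the plan says.** Protocol 4.3.5 gives two relevant grounds for withdrawal. The first is ineligibility: "If a patient who does not meet the enrollment criteria is inadvertently enrolled, that patient should be withdrawn from the study". The sentence that follows covers a patient who has already received ANB020 or placebo, and requires that "the patient must be followed up until EOS (Day 127) for any AEs and/or SAEs". So the rule reaches dosed patients, and the only follow-up it names for them is safety follow-up. The second ground is "Lack of compliance with protocol", listed among the circumstances in which patients will be withdrawn. It has no threshold and no time limit. The first item in the same list, by contrast, is expressly confined to the period before the infusion.

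Protocol 5.6 fixes the treatment: "Patients will receive a single dose of ANB020 or placebo administered under supervision at the study center".

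Patients who stop early have an ET visit. According to the footnotes of Protocol Table 4.1, "ET visit will include all procedures to be done at EOS visit", and these procedures include eosinophils, FEV1, FeNO and ACQ. In the visit list of SAP Appendix 2, ET shares a row with the final visit, under a label that begins "Day 127, week 18 (EOS/ET". SAP 6.4 (Windowing Conventions) is marked as not applicable.

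On replacement, Protocol 9.1 says "All patients who discontinue the study prior to completing the Day 36 study assessments will be replaced". Withdrawals after Day 36 are not replaced. Protocol 9.4.3 and SAP 7.3 and 20 plan no imputation of missing outcome values.

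**The concern.** In a multiple-dose trial, withdrawing a patient may at least end exposure. Here exposure is complete on Day 1, so withdrawal for ineligibility or non-compliance can only end measurement. For the ineligible patient the study keeps contact to Day 127 but no longer asks for the outcome measurements that the trial exists to collect.

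The two grounds differ in kind. Eligibility is fixed at or before dosing, so removing patients on that ground mainly costs information. Compliance is judged after randomisation and may follow the course of the disease, so removal on that ground could leave values missing for reasons tied to outcome. The MMRM is valid if missingness is explained by the observed data, and nothing in the plan tests that condition. Replacing an early withdrawal restores the count but not the patient who was randomised. In a trial of about 24, a few such decisions matter.

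**Working it through.** **No plan figure to reproduce.** Protocol 9.1 says the number of patients is not based on power. The documents give no effect size, SD or dropout rate. The arm size of 12 comes from Protocol 6.2.2.

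**What is not collected.** Table 4.1 has eight post-baseline clinic visits: Days 2, 8, 22, 36, 64, 85, 106 and 127. The number of later scheduled visits after the last one attended is:

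| Last visit attended | Later scheduled visits |
|---|---|
| Day 2 | 7 |
| Day 8 | 6 |
| Day 22 | 5 |
| Day 36 | 4 |
| Day 64 | 3 |
| Day 85 | 2 |
| Day 106 | 1 |

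The same counts hold for ACQ, which is omitted only on Day 2. One ET assessment is gained in each case.

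**Which endpoints are exposed.**
- Day 22 eosinophils (primary): lost only if withdrawal comes before Day 22 and the ET visit does not fall at that time.
- Day 127 eosinophils, FEV1 and FeNO (secondary): the true Day 127 value is missing after every earlier withdrawal. The ET reading carries the combined EOS/ET label whatever its actual day. After withdrawal at Day 36, for example, it could be up to 127 − 36 = 91 days early. The SAP's eosinophil table shell is titled Day 127/ET. The FEV1 and FeNO shells are titled Day 127 only, so how ET values enter those two analyses is not stated outright.

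**What is kept.** The full analysis set (Protocol 9.1.1, SAP 5.3) needs dosing and one post-baseline eosinophil count, and has no exclusion for withdrawal. The MMRM in SAP 20 uses each post-dose time point observed.

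**Precision, as an illustration.** Assume k patients in one arm are lost and not replaced. One patient is 1/12 = 8.3% of an arm. The standard error relative to 12 v 12 is

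sqrt((1/12 + 1/(12 − k)) / (2/12)).

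- k = 2: sqrt((1/12 + 1/10)/(2/12)) = sqrt(1.100) = 1.049, a rise of about 5%.
- k = 3: sqrt((1/12 + 1/9)/(2/12)) = sqrt(1.167) = 1.080, a rise of about 8%.

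A patient lost before Day 22 is also lost before Day 36 and is replaced. If replacement is completed, these figures therefore do not describe the primary endpoint. They fit the Day 127 comparison when patients leave after Day 36. They ignore the baseline covariate and the earlier repeated measures, which would recover part of the loss in an MMRM.

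**The case against.** The strongest reply is that little is lost. Withdrawal removes nothing already recorded, the ET visit adds a complete assessment, and the primary endpoint falls only three weeks after dosing, with replacement for anyone who leaves before Day 36. Investigator and sponsor are blinded, and eligibility is checked before dosing, so ineligibility withdrawals have no obvious link to arm or outcome. Protocol 4.3.5 requires safety follow-up but does not forbid other measurements. All of this is correct and sets the size of the point.

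Two stronger readings are tempting and are not supported.

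- A reader might infer that withdrawal discards a patient's primary and efficacy data. It does not, because the full analysis set and the MMRM keep the observed visits. Collected eosinophil data can be excluded, but by other rules: the PD analysis set (Protocol 9.1.1, SAP 5.6), on which the primary endpoint is analysed, and the major-deviation rule in SAP 11. Both depend on a deviation affecting the PD data, not on withdrawal.
- A reader might infer that a patient who takes systemic steroids above the stated limit for worsening asthma is thereby withdrawn, which would tie loss directly to outcome. Protocol 5.8.1 says only that "Use of these excluded medications is a protocol deviation and should be recorded", and 5.8.2 leaves oral prednisolone to the treating physician's discretion. Withdrawal would follow only if such use were counted as lack of compliance, which is not defined. Sections 5.8.1 and 5.8.2 should be reconciled with each other, as a separate matter.

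What the reply does not answer is that the remaining loss serves no purpose. The ET reading does not stand in for Day 127, and replacement does not bring back the randomised patients.

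**Conclusion.** The point holds as an avoidable source of missing data written into the protocol, and correcting it is a cheap improvement. Following 4.3.5 as written stops scheduled eosinophil, FEV1, FeNO and ACQ measurement after one ET visit in dosed patients who could still be measured. The Day 127 endpoints bear most of the effect; the Day 22 primary endpoint is exposed only to withdrawals in the first three weeks.

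The size cannot be fixed from the documents, because the number of such patients is not given. The 5% and 8% rises in standard error rest on an assumed two or three unreplaced losses in one arm. Bias is possible through the compliance ground, but the documents do not show that it will occur or that it would differ by arm.

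**What to change.** In Protocol 4.3.5, state that every dosed patient who still consents remains on the scheduled assessments to Day 127. After dosing, ineligibility or non-compliance should be recorded as a deviation and should not be a ground for withdrawal. Leave in place the existing provisions for withdrawal of consent, safety or best-interest reasons, pregnancy, and the investigator or sponsor stopping the study. This changes what is measured, not how patients are treated.

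In the SAP, keep these patients in the full analysis set analyses, and analyse eosinophils in all randomised dosed patients alongside the PD analysis set. Without that second step, the PD-set and major-deviation rules could still exclude the measurements that the protocol change preserves.

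The cost is wording in both documents and a few clinic visits that are already on the schedule. Those visits would be extra for patients who would otherwise have safety contact only, since 4.3.5 does not say that this contact takes place in clinic.
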